3.2 Primary Study Endpoints

The primary endpoint is to determine whether those treated with anakinra for 84 days demonstrate an improved hearing threshold compared with their pre-anakinra-treatment threshold.

3.3 Primary Safety Endpoints

The safety endpoints to be measured include:

- 1. assessment for neutropenia,
- 2. assessment for development of severe new infections while on therapy,
- 3. assessment of injection site irritation,
- 4. assessment of worsening of hearing thresholds while on therapy.

4 Subject Selection and Withdrawal

4.1 Inclusion Criteria

1. Patients must have Autoimmune Inner Ear Disease, Meniere's Disease, or Sudden Sensorineural Hearing Loss with autoimmune features.

CONFIDENTIAL This material is the property of the Feinstein Institute for Medical Research, North-Shore-LIJ Health System. Do not disclose or use except as authorized in writing by the study sponsor

- 2. Age and Gender: males and females ages 13 to 75 weighing 90 lbs or greater will be recruited.
- 3. Patients must be capable of understanding and giving informed consent.
- 4. If the recruited patient is between the ages of 13 and 17, an assent will be obtained from the patient and consent from one parent/legal guardian prior to enrollment.
- 5. Patients must have SNHL of greater than 30dB at one or more frequencies in one or both ears with evidence of active deterioration (elevated threshold) in at least one ear of 15 dB at one frequency (excluding 250 or 8kHz as a sole indicator) on their audiogram, or 10dB at 2+ frequencies developing in >3 days but <90 days, or in the case of SSNHL, the hearing loss may evolve in less than 3 days if the patient displays features suggestive of an autoimmune disorder.
- 6. Patients must have previously undergone a trial of high-dose corticosteroid therapy, at 60 mg daily for a minimum of seven days, with a variable taper thereafter that consists of a total of 30 consecutive days of corticosteroid use. Patients must have demonstrated less than or equal to a 5 decibel average improvement in their PTA in response to corticosteroids as measured by their audiogram.
- 7. Patients may have a concurrent other autoimmune disease(s).

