- **Definition of corticosteroid non-responder**: All patients must have been treated with 60mg of oral prednisone for a minimum of 7 days with a variable taper thereafter, for a minimum of 30 days in total, and response to prednisone therapy measured by audiometry before treatment and at approximately 30 days post-treatment. Audiometry will consist of a pure tone average ((PTA): here to include 250, 500, 1000, 2000, and 4000Hz) and speech discrimination score to be recorded pre and post treatment. Clinical responsiveness will be defined as either an average of 5 decibel or greater PTA improvement (as the average of five frequencies was recorded) in their post-treatment audiogram, or a greater than 12% improvement in the speech discrimination scores. In the event a patient with a pre-treatment profound SNHL demonstrates an improvement on PTA, however, no improvement in speech discrimination is noted, and the initial speech discrimination is 0%, this patient would be classified as a non-responder. Patients that received concurrent or sequential intratympanic corticosteroids may be included only if they received the 30 days of oral steroids as well.
- *Entrance into the research protocol:* Patients that failed to respond to corticosteroid therapy will be offered anakinra therapy as an alternate therapy to continued corticosteroid therapy. Given that anakinra is a daily subcutaneous injectable, it is unethical to perform a placebo controlled trial where a patient potentially could receive 84 consecutive days of injectable saline. Moreover, the total projected number of patients for this phase I/II trial is too low to consider a cross-over design. Thus an open-label trial design is proposed. Patients will be monitored every 28 days while on therapy

by audiogram and laboratory values. Laboratory values include a Complete Blood Count (CBC) with differential, SMA-7, HCG or UCG (for child-bearing aged females) and plasma IL-1 β levels/stimulation studies. Patients will complete daily logs as to injection site reactions and other potential side effects.

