5.9.4 Return or Destruction of Study Drug

At the completion of the study, there will be a final reconciliation of drug shipped, drug consumed, and drug remaining. This reconciliation will be logged on the drug reconciliation form, signed and dated. Any discrepancies noted will be investigated, resolved, and documented prior to return or destruction of unused study drug. Drug destroyed on site will be documented in the study files.

6 Study Procedures

All patients will initially be treated with a 30-day course of corticosteroids. Only those patients that failed to respond to corticosteroids (as defined in section 3.1) will be approached to enroll in this clinical trial. The option to undergo treatment with Anakinra for a corticosteroid resistant hearing loss will be explained to the patient. The sponsor-investigator, [name], has a Conflict of Interest (COI) and will not directly consent patients from her practice. The nature of the conflict is that she and the Feinstein Institute hold a use patent for interleukin-1 antagonist therapy for autoimmune and sudden hearing loss as well as Meniere's disease. This conflict will be disclosed to all patients considering participation in this study. Any patients designated appropriate for study by the inclusion/exclusion criteria will be consented by her partner, [name], who does not have a COI. The other study investigators ([name] and [name]) have no COI and therefore will be able to consent patients from their own practices. Risks and potential benefits of anakinra therapy will be described.

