7.1 Sample Size Determination & Statistical Methods

Corticosteroid resistant AIED patients currently have no therapeutic alternatives available to them. These patients that failed initial corticosteroid therapy are not expected to demonstrate a placebo effect, as they have already undergone 2 serial audiograms that demonstrated a <5dB PTA improvement in hearing for trial inclusion. A Simon 2-stage "optimal" design will be used to test the null hypothesis that the true objective response rate (RR) is 10% or less (which would not be clinically meaningful) versus the alternative hypothesis that the true response rate is 30% or greater. With a significance level of 0.05 and a power of 0.80, a maximum total of 29 evaluable patients will be required to assess the objective response rate. Ten (10) evaluable patients will be enrolled in Stage 1(R21 phase). If 1 or fewer objective responses are observed in the first 10 evaluable patients, then the trial will be terminated (do not proceed to R33). Primary milestone: If 2 or more objective responses (improvement in the PTA \geq 5dB) are observed in the first 10 patients (20%), we will proceed to the R33 phase.

If the RR is 10% or less, then the expected sample size for the trial is 15 patients and the probability of early termination at the end of the R21 phase (stage 1) is 74%. Overall, a total of approximately 38 patients may be enrolled in this R21/R33 study to ensure that the specified numbers of evaluable patients are available for analysis at each stage.

Given that anakinra may cause injection site reactions, it is possible that some patients will prematurely self-terminate the study. In order to appropriately evaluate the results, 29 patients would need to complete the 84-day course of anakinra. Overall, a total of 38 patients may be enrolled in this study to ensure that the specified numbers of evaluable patients are available for analysis at each stage.

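### Corticosteroid non-response, the condition that defines the trial population, is stated in three incompatible ways in sections 3.1, 4.1 and 7.1

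*Protocol*

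**What the plan says.** Four places in the protocol bear on who counts as corticosteroid-resistant.

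- **Section 3.1** (definition of corticosteroid non-responder) has two routes to response: "Clinical responsiveness will be defined as either an average of 5 decibel or greater PTA improvement", "or a greater than 12% improvement in the speech discrimination scores". It adds an exception. If a patient with profound loss before treatment gains on PTA but not on speech, "and the initial speech discrimination is 0%, this patient would be classified as a non-responder".
- **Section 4.1 item 6** is the formal inclusion criterion: "Patients must have demonstrated less than or equal to a 5 decibel average improvement in their PTA in response to corticosteroids". It mentions neither speech nor the exception.
- **Section 7.1** describes those enrolled as having had "2 serial audiograms that demonstrated a <5dB PTA improvement in hearing for trial inclusion". It too mentions neither speech nor the exception.
- **Section 6** (opening paragraph) says: "Only those patients that failed to respond to corticosteroids (as defined in section 3.1) will be approached to enroll in this clinical trial".

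Two more places define response to anakinra. Section 7.1 counts a PTA gain of 5 dB or more as an objective response and gives speech no role. Section 7.2 describes the primary analysis as improvement in either audiometric threshold or speech discrimination, with no cut-off for either.

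**The concern.** The trial asks whether anakinra restores hearing in patients whom prednisone did not help, so the definition of steroid failure fixes the population to which the answer applies. It also carries statistical weight. The trial has no control arm, and section 7.1 argues that no placebo effect is expected because entry required less than 5 dB of improvement on serial audiograms. The inclusion list does not enforce that rule: it lets in exactly 5 dB and ignores speech.

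If sites apply item 6 as written, some patients whom 3.1 calls steroid responders can enter. Others, whom 3.1 calls non-responders, are turned away. Two screeners who each follow the protocol could decide differently on the same patient.

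**Working it through.** **The plan's own figures.** For the two-stage design in section 7.1 (10% against 30%, significance level 0.05, power 0.80, 10 patients in stage 1, stop at 1 or fewer responses, maximum 29):

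- Probability of early termination at 10% = P(0 of 10) + P(1 of 10) = 0.3487 + 0.3874 = 0.736. The plan says 74%.
- Expected sample size = 10 + (1 − 0.736) × 19 = 15.0. The plan says 15.
- An exact search for the optimal design returns the same 10 and 29. It stops at 1 or fewer responses in stage 1 and calls the drug inactive at 5 or fewer of 29, with type I error 0.047 and power 0.805.

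The arithmetic is sound. What is in question is who the 29 patients are.

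**The definitions applied to the same patients.** Each row is a change on prednisone.

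| Change on prednisone | 3.1 | 4.1 item 6 | 7.1 restatement |
|---|---|---|---|
| PTA gain exactly 5 dB | responder | met | not met |
| PTA gain under 5 dB, speech gain above 12% | responder | met | met |
| Profound loss, 0% initial speech, PTA gain above 5 dB, no speech gain | non-responder | not met | not met |

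In the third row all the listed conditions are needed, and the patient must also escape exclusion 7 in section 4.2, which removes immediate-onset profound loss with 0% speech discrimination. Only the remainder is affected.

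**Effect of section 6.** It restricts the approach to 3.1 non-responders, so the first two rows are never approached if it is followed. The third row is approached and then fails item 6.

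**How common is exactly 5 dB?** The protocol gives no distribution of PTA change, so this is an illustration. Assume that thresholds are read in 5 dB steps. The mean of five frequencies then moves in steps of 5/5 = 1 dB, and exactly 5 dB is an attainable value. Assume also that the change is roughly Normal, and take P(4.5 to 5.5 dB) = Φ((5.5 − m)/s) − Φ((4.5 − m)/s).

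| Mean m (dB) | SD s (dB) | P(exactly 5 dB) |
|---|---|---|
| 0 | 4.24 | 0.047 |
| 0 | 6 | 0.047 |
| 0 | 8 | 0.041 |
| 2 | 4.24 | 0.073 |
| 2 | 6 | 0.059 |
| 2 | 8 | 0.046 |

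The range is about 4 to 7% of steroid-treated patients. Among those with a gain of 5 dB or less, the share is P divided by Φ((5.5 − m)/s), about 5 to 9% on the same grid. Neither figure allows for screening under section 6. The speech-only group in the second row cannot be sized at all from the protocol.

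**The case against.** The strongest reply is that the protocol should be read as a whole. Section 6 admits only 3.1 non-responders to the approach, and section 4.3 requires both steroid failure and the inclusion and exclusion criteria. On that reading 3.1 is a gate ahead of 4.1, and the first two groups never enter. This stands as a limit on how many such patients would be enrolled. It does not reconcile the text: item 6 sets a different rule for the same condition, 7.1 gives a third, and the exception patients pass the section 6 gate only to fail item 6.

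A reader might infer three stronger things, which the protocol does not support.

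- **That boundary patients could decide the stage 1 gate.** The time 0 audiogram is the one at the end of steroid treatment (section 6.1), so a 5 dB gain on prednisone is already in the baseline. A further 5 dB is needed to count as a response to anakinra. At 4 to 7%, 10 patients would include about 0.4 to 0.7 at the boundary, and only some of those would gain again.
- **That the rules systematically favour anakinra over prednisone.** Sections 3.1 and 7.1 both count 5 dB or more as response. On speech, 3.1 credits prednisone with a gain above 12%, while the 7.1 objective response gives anakinra no such credit. Nor does the trial compare the two drugs.
- **That the false-positive rate is inflated.** With the same design, a no-effect rate of 12% or 15% instead of 10% would raise the chance of a positive trial from 4.7% to 9.5% or 20.1%. Nothing in the protocol links this inconsistency to a shift of that size, and continued recovery after steroids is a possibility for which the protocol gives no figure.

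**Conclusion.** The point holds as an internal contradiction in the trial's defining eligibility condition. Sections 3.1, 4.1 item 6 and 7.1 cannot all be right, and section 6 sides with 3.1 without resolving the conflict. That 3.1 responders can enter is true only where item 6 is applied on its own; the documents do not support saying that they will be enrolled.

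The consequence that does follow concerns the 7.1 argument. Its expectation of no placebo effect, on which an uncontrolled trial depends, cites an entry rule that the inclusion list does not enforce. The number of patients affected cannot be computed from the protocol. The 4 to 7% for exactly 5 dB rests on assumed 5 dB steps, a Normal shape, an SD of 4.24 to 8 dB and a mean of 0 to 2 dB. It counts patients at the boundary, not responses to anakinra. The sample size calculation is unaffected. The text should be corrected because eligibility ought to have one reading and the repair is cheap.

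**What to change.** Reconcile sections 3.1, 4.1 item 6, 6 and 7.1 to one definition of corticosteroid non-response. Section 6 already names 3.1 as the reference, so the simplest drafting is for item 6 and the 7.1 restatement to refer to the 3.1 definition in full (the PTA limit, the speech criterion and the 0% speech exception) instead of paraphrasing it. If the investigators want a different clinical rule, they should write it once in 3.1 and have the other sections point to it.

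Separately, reconcile response to anakinra between 7.1 (PTA gain of 5 dB or more only) and 7.2 (threshold or speech discrimination, no cut-off), so that the response counted in the two-stage design is the one analysed.

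The cost is wording. Section 3.1 already requires PTA and speech discrimination to be recorded before and after prednisone, so no new data are needed. The downside is that a few borderline patients change eligibility status, in either direction.

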4.2 Exclusion Criteria

- 1. Patients over 75 years of age, because there is a higher incidence of infections in the elderly population in general, caution should be used in treating the elderly.
- 2. Patients with evidence of retrocochlear pathology (vestibular schwannoma) or inner ear malformation (Mondini Malformation or Enlarged Vestibular Aqueduct) based on imaging.
- 3. Patients concurrently receiving methotrexate or TNF-antagonist therapy.
- 4. Patients with a diagnosis of any immunodeficiency syndrome.
- 5. Patients with active or chronic infections.
- 6. Patients currently receiving, or having received treatment for a malignancy in the past three years.
- 7. Patients that developed an immediate onset, profound SNHL with 0% speech discrimination scores.
- 8. Patients whose hearing loss coincided with significant, disabling episodes of vertigo.
- 9. Patients with a diagnosis of chronic renal insufficiency (a creatinine clearance of <49mL/min) or chronic renal failure.
- 10. Patients with evidence of neutropenia (an ANC of < 1000) prior to treatment with Anakinra.
- 11. Patients with known hypersensitivity to E. coli derived products.
- 12. Patients with latex sensitivity (the needle cover is a derivative of latex).
- 13. Pregnant or lactating females.
- 14. Children under the age of 13, as Anakinra is supplied in pre-filled syringes dosed for adult sized patients..
- 15. Non-English speaking patients, as the word recognition scoring is in English and is a vital component to the efficacy analysis.

4.3 Subject Recruitment and Screening

Subjects will be recruited from the practices of several Neurotologists and Otolaryngologists from the North Shore-LIJ Health System. No recruitment materials will be disseminated; however, patients within these practices with a diagnosis of AIED, SSNHL or Meniere's Disease may be sent letters informing them of this clinical trial. All patients that are treated with corticosteroids (60mg per day for 7 days with a taper thereafter to 30 days of treatment in total) will be informed of the study availability to them only if they fail to respond to corticosteroids as measured on the audiogram at approximate 30 day post-treatment interval. The study will be described to the patient. Pre-treatment laboratory tests will be performed for inclusion (CBC, SMA-7, beta HCG or UCG (if female of child-bearing age)) at visit 1 (or within 2 weeks prior). Plasma IL-1 β and in vitro expression of IL-1 β in PBMC and monocytes will also be measured. Patients that fail corticosteroid therapy and meet inclusion and exclusion criteria will be given the option of enrolling in this phase I/II trial and receiving Anakinra. Alternatively, they may opt to receive continued corticosteroids, or no further treatment. It is possible that a number of patients will not wish to perform daily injections for 84 days.

Some patients that failed corticosteroid therapy (as measured by a pre and post treatment audiogram) may be referred by non-study physicians for participation in this study. Inclusion of these patients may be considered if no greater than 30 days has elapsed since the discontinuation of corticosteroids, and that the patient received 30 days of prednisone. In the event the patient did not receive 30 days of prednisone, the patient will be treated again with 60mg of prednisone for 7 days and a variable taper to achieve 30 days of continuous therapy. Audiometry will be repeated again at the end of the treatment. If the patient is still a "non-responder", they will have the option to enroll in this study.

4.4 Early Withdrawal of Subjects

4.4.1 When and How to Withdraw Subjects

Some patients may be prematurely withdrawn prior to completion of the drug for several reasons. Indications for early termination of anakinra administration is (1) Development of neutropenia as defined as an ANC of <1000, (2) Development of a serious bacterial infection (pneumonia, cellulitis, septicemia) (3) Severe injection site reaction, (4) Rash consistent with an allergic reaction to Anakinra, (5) Significant worsening of hearing threshold in either ear (greater than 20dB worsening of the pure tone average) (6) Development of renal insufficiency (as determined by a creatinine clearance of <49mL/min). The patient may also self-withdraw due to intolerance of daily injections. Although abrupt termination of drug should not pose a safety issue, a greater concern exists for hearing deterioration. If this occurs, prednisone therapy will immediately be reinstituted, barring any patient contraindications to continued corticosteroid therapy. If anakinra therapy is terminated due to safety concerns, corticosteroid therapy may be recommended, only if further hearing deterioration occurs off anakinra. Also see section 9.5: Stopping Rules. If a patient is withdrawn during study treatment, a follow-up audiogram, all safety bloods and IL-1 levels will be done approximately within 30 days of the last injection.

4.4.2 Data Collection and Follow-up for Withdrawn Subjects

Even if patients prematurely withdraw, or are withdrawn from the study, an analysis of all data collected through the time of withdrawal will be included for analysis. Data on the withdrawn

CONFIDENTIAL This material is the property of the Feinstein Institute for Medical Research, North-Shore-LIJ Health System. Do not disclose or use except as authorized in writing by the study sponsor subjects is critical to the integrity of the final data analysis, especially for safety and tolerability issues.

5 Study Drug

5.1 Description

Anakinra is supplied in pre-filled syringes for daily subcutaneous injection. One box represents a 28 day supply. Anakinra is to be stored at 4^{0} C. The drug should be allowed to reach room temperature prior to injecting. One pre-filled syringe contains 100mg of anakinra suspended in solution.

5.2 Treatment Regimen

The patient will inject the entire contents (100mg) of a prefilled syringe subcutaneously after appropriately sterilizing the area to be injected with rubbing alcohol and allowing the area to dry. The patient will perform daily injections for 84 consecutive days.

5.3 Method for Assigning Subjects to Treatment Groups

This open-label trial of Anakinra will not be randomized. Given the route of drug delivery, a placebo-controlled trial is not possible. All patients that fail corticosteroid therapy will be offered Anakinra, thereby avoiding selection bias for certain patients. All enrolled patients on Anakinra will undergo audiometric testing and blood collection at 0, 28, 56 and 84 days during the treatment period. Upon cessation of treatment, audiometric testing will again be performed at +30, +90 days and +180 days. During the same visit as audiometric testing, blood will be collected for a CBC, SMA-7, and IL-1 β plasma and stimulation studies.

5.4 Preparation and Administration of Study Drug

The drug, Anakinra, will be supplied by the manufacturer and stored in the LIJ pharmacy department. The pre-filled syringes do not require reconstitution or mixing. The lot number will be recorded and the box (28 syringes for a 28 day supply) dispensed by one of the study nurses. The study nurse will demonstrate to the patient how to inject the drug properly. The patient will also watch an instructional video. The patient will be given a sharps container to store the wasted syringes. These sharps containers will be returned to us for disposal.

5.5 Subject Compliance Monitoring

Patients will be given a 28 day supply of medication, record keeping materials and a sharps container. The patient will be asked to send an email (at least weekly) to the study nurse indicating the time of injection and any noted skin or other reactions while on study drug. If the study nurse has not been contacted by the enrolled subject in a 7 day period, the nurse will contact the patient by telephone to check their status. If the patient will be without email access for a given period, this information will be conveyed to the nurse prior to the period, and the patient will fill out a written log book during this period. In the event the patient does not have email access, the patient will fill out a log book daily. The study nurse will contact these patients weekly (by phone) to check their status. It is anticipated that the majority of subjects will communicate by email. Compliance will also be monitored by having the patient return the sharps container monthly. Although spent needles will not be pulled out and counted, the

volume of needles in the container can be estimated. In the event a patient is non-compliant, the patient will be contacted by the physician that enrolled the patient. The physician will determine the cause of non-compliance. For any patient that has a greater than 72 hour lapse in treatment not dictated by a physician, in most cases, these subjects will be informed that they will be withdrawn from the study.

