5.9.3 Dispensing of Study Drug

Anakinra will be dispensed to enrolled patients by providing them with a 28 day supply and a sharps container for used syringes. The patient will complete daily logs of drug administration. Upon the completion of the 28 day course, the patient will return to the office with the filled sharps container and any unused medication. This reconciliation process will be completed before providing the patient with the next 28-day course of medication.

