7.2 Subject Population(s) for Analysis

All-Treated Population: The analysis will be performed on all corticosteroid non-responders subsequently treated with 84 consecutive days of anakinra. The primary analysis will consist of determining whether an improvement in either audiometric threshold or speech discrimination can be achieved with anakinra in patients that did not respond to corticosteroids. The secondary analysis will be to determine whether anakinra can be administered safely for an 84 consecutive day period without significant complications in this patient population.

8 Safety and Adverse Events

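### The protocol does not settle whether a patient with a dosing lapse counts in the response rate: sections 4.4.2, 5.5, 7.1 and 7.2 give different answers, and section 5.5 leaves longer lapses to judgement

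*Protocol*

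**What the plan says.** Five places in the protocol bear on this.

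- **Section 5.2** gives the regimen: "The patient will perform daily injections for 84 consecutive days".
- **Section 5.5** deals with lapses: "For any patient that has a greater than 72 hour lapse in treatment not dictated by a physician, in most cases", and it continues "these subjects will be informed that they will be withdrawn from the study". The inquiry belongs to the physician who enrolled the patient: "The physician will determine the cause of non-compliance". The section sets no limit on gaps that a physician directs, and no criterion for the cases in which a longer lapse is excused.
- **Section 7.1** sizes the trial in evaluable patients (10 in Stage 1, 29 in all) and adds that "29 patients would need to complete the 84-day course of anakinra".
- **Section 7.2**, under the label of an all-treated population, says: "The analysis will be performed on all corticosteroid non-responders subsequently treated with 84 consecutive days of anakinra".
- **Section 4.4.2** says that data collected up to withdrawal enter the analysis. It stresses safety and tolerability but does not confine the statement to them.

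Section 4.4.1 already requires a follow-up audiogram within about 30 days of the last injection for a patient withdrawn during treatment.

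**The concern.** A daily schedule and a tolerance for missed doses can live together. The difficulty is that sections 7.1 and 7.2 use completion of the course to decide who is counted, while section 5.5 decides who stays on study by a looser and partly discretionary standard. Section 4.4.2 adds a third rule. A patient who missed two doses, had a physician-directed gap, or was excused a longer lapse remains on study under section 5.5. No passage says whether that patient is a completer, is evaluable, or occupies one of the first 10 places.

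The trial is open-label with audiograms at days 28, 56 and 84. For any lapse after day 28, an on-treatment hearing result already exists when the decision to keep or withdraw is made. Even for an earlier lapse, whether the patient counts among the evaluable can be settled once hearing results are known. Such judgement can move the response rate either way. With a Stage 1 rule of 2 in 10, one reclassified patient can reverse the decision to continue.

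**Working it through.** **Inputs, all from section 7.1:** null rate 0.10, alternative 0.30, alpha 0.05, power 0.80, Stage 1 of 10 with a stop at 1 or fewer responses, maximum 29 evaluable, 38 enrolled. The final boundary is not stated. A search for the optimal Simon design gives success at 6 or more of 29, and that is used here.

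**1. Reproduce the design.**
- Probability of early termination at 10% = 0.9^10 + 10 × 0.1 × 0.9^9 = 0.3487 + 0.3874 = 0.736 (stated 74%).
- Expected sample size = 10 + 19 × (1 − 0.736) = 15.0 (stated 15).
- Probability of success at rate p = sum over x = 2 to 10 of P(X1 = x) × P(X2 ≥ 6 − x), with X1 ~ Bin(10, p) and X2 ~ Bin(19, p). This gives 0.0471 at p = 0.10 and 0.805 at p = 0.30.

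The plan's figures hold.

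**2. How often one patient matters in Stage 1.** The results next to the boundary are exactly 1 or exactly 2 responses in 10.
- At 10%: 0.3874 + 0.1937 = 0.58.
- At 30%: 0.1211 + 0.2335 = 0.35.

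These are chances that the result lies where one patient could tip it, not chances that a patient is reclassified.

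**3. Effect of selective loss (illustration).** Assume a true rate of 10%, that a fraction f of non-responders is classed as non-completing and replaced, and that no responder is lost. The rate among those counted is p' = 0.1 / (0.1 + 0.9 × (1 − f)).

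| f | p' | Stage 1 passed | Type I error |
|---|---|---|---|
| 0 | 0.100 | 0.264 | 0.047 |
| 0.10 | 0.1 / 0.91 = 0.110 | 0.302 | 0.068 |
| 0.20 | 0.1 / 0.82 = 0.122 | 0.349 | 0.101 |

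The f = 0.20 case fits the planned enrolment: 0.9 × 0.20 = 18% of 38 is about 7 patients, and 38 − 29 = 9 places are spare. Losing responders instead would push the rate down.

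**4. The same patient under each section.**

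| Patient | 5.5 | 7.2, read literally | 4.4.2 |
|---|---|---|---|
| Gap of 72 hours or less | stays | not 84 consecutive days | not addressed |
| Physician-directed gap | stays, no limit given | not 84 consecutive days | not addressed |
| Longer lapse, excused | stays, no criterion | not 84 consecutive days | not addressed |
| Longer lapse, withdrawn | withdrawn | outside the population | data included |

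**The case against.** The strongest reply is that the phrase in section 7.2 describes course length and not perfect adherence. The Study Summary speaks of an 84-day duration, section 7.1 of completing the course, and the population is labelled all-treated. No passage says that one missed dose disqualifies anyone, and detail on evaluability may sit in an SAP that is not shown. This reading is reasonable and removes part of the conflict. It does not say how an excused or physician-directed gap is counted, and it leaves sections 7.2 and 4.4.2 apart on withdrawn patients. Those rules are in the protocol itself.

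Four stronger readings are tempting and are not supported.

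- **That 29 of 38 is out of reach.** With no missed dose allowed and independent daily adherence of 0.98, 0.99 or 0.995, about 7, 16 or 25 of 38 would qualify (38 × 0.98^84, and so on). Those adherence values are not in the protocol, independence is an assumption, and zero tolerance is the least plausible reading.
- **That drug supply makes lapses likely.** Boxes hold 28 syringes, and of the returned-drug check section 5.9.3 says "This reconciliation process will be completed before providing the patient with the next 28-day course of medication". A late visit could therefore leave a fully adherent patient without drug, but nothing shows that visits will run late.
- **That physician-directed gaps are unlimited.** The protocol is silent on a limit; it does not grant one without end.
- **That the sponsor-investigator's patent drives the decision.** Section 6 has investigators without a conflict consent the patients, and section 5.5 gives the inquiry to the physician who enrolled the patient. Section 8.6.1 gives an independent board access to compliance logs and audiometric data.

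Other safeguards are real but partial. Audiologists are blinded to timepoint (section 6.1), which protects the measurement and not the choice of who is counted. Weekly contact (section 5.5) means that some lapses surface before any on-treatment audiogram. The board is not assigned the decision on evaluability.

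**Conclusion.** The point holds in limited form. The protocol makes completion decide who is in the response rate, gives differing rules for patients with lapses or withdrawals, and leaves some of these patients to judgement that can follow open-label audiograms. It should be corrected, because the Stage 1 decision rests on a difference of one patient in 10.

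The size is conditional. The rise in type I error from 0.047 to about 0.07 or 0.10 assumes a true rate of 10%, loss of non-responders only (10% or 20% of them), and a final boundary of 6 of 29. It shows one adverse direction and does not predict how many patients will lapse. If the Study Summary's 30% is meant as an observed bar at the end, these error rates would be lower; the Stage 1 probabilities do not depend on it.

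**What to change.** - Reconcile sections 4.4.2, 5.2, 5.5, 7.1 and 7.2. The permitted lapse, physician-directed gaps and the withdrawal rule are for the sponsor to set; the passages need to agree.
- In section 7.2, replace the requirement of 84 consecutive days with one definition of the primary population that does not depend on discretionary completion. Use the same definition for evaluable in section 7.1, at both stages.
- Count patients with lapses, and those withdrawn for non-compliance, in the primary response rate by a rule stated in advance. For withdrawn patients, use the audiogram that section 4.4.1 already requires, or count them as non-responders if there is none. The rule should also say how an audiogram taken after prednisone was restarted is counted, since section 4.4.1 provides for that treatment.
- Classify dosing from the patient logs and the unused-drug reconciliation, without reference to audiograms. A count of used syringes is not available, because section 5.5 says that spent needles are only estimated by volume.

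The cost is mainly protocol wording, and the audiogram after withdrawal is already planned. The response rate may come out slightly lower because patients with imperfect dosing are counted.
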